5. AMENDMENTS AND UPDATES

None

6. MILESTONES

Milestone	Planned Completion Date
Internal approval of study synopsis	March 2020
Internal approval of study protocol	May 2020
Submission of study protocol to FDA	May 2020
FDA feedback received	June 2020
Finalization of protocol	July 2020
IRB submission and review	July 2020
Recruitment & data collection	Q3/Q4 2020
Demographics & clinical characteristics	November 2020
Outcomes assessment	November 2020
Final report	December 2020

7. RATIONALE AND BACKGROUND

The epidermal growth factor receptor (*EGFR*) signaling pathway regulates apoptosis and proliferation in normal cells. An *EGFR* family component of the of tyrosine kinase ligands, neuregulin-1 (*NRG1*), induces the proliferation, differentiation, and survival of cells in epithelial, neuronal, and myocytic tissue types, among others. The first *NRG1* fusion was reported by Fernandez-Cuesta et al. in 2014 when they identified five *CD74-NRG1* fusions in invasive mucinous adenocarcinoma (IMA).[1] The *CD74-NRG1* fusion provides an extracellular anchor for the epidermal growth factor (EGF) domain of *NRG1* to bind to ErbB3 (HER3) leading to HER3 heterodimerization and activation of downstream signaling pathways leading to oncogenesis.[2] As such, targeted treatment with inhibitors of this pathway represents a possible therapeutic strategy. Afatinib, a pan-ErbB inhibitor has been evaluated in preclinical models[3] and in several case reports in patients with tumors harboring a *NRG1* fusions that achieved durable benefit with afatinib.[4-6]

NRG1 fusions are rare, with an estimated overall frequency of ~0.2% across solid tumors[7] and have a reported prevalence of up to 31% in lung IMA[8] making prospective clinical trials challenging. In addition to IMA, other tumor types with *NRG1* gene fusions that have been described include cholangiocarcinoma (0.8% of cases tested), thyroid cancer (0.7%), ovarian cancer (0.5%), pancreatic cancer (0.4%), non-small cell lung cancer (NSCLC; 0.3%), breast cancer (0.2%), sarcomas (0.2%), and sinonasal teratocarcinoma,[9] as well as renal cell carcinoma, head and neck cancer, uterine cancer, and prostate cancer.[10] While the incidence of *NRG1* gene fusions is only around 0.2% of all solid tumors, this represents approximately 3,500 new cases per year.

Results presented at the American Association for Cancer Research (AACR) Annual Meeting 2019 showed tarloxotinib to be active against *NRG1* gene fusion cancers, irrespective of site of origin. It is believed that afatinib may have similar activity across sites of cancer associated with *NRG1* gene fusions. Recent case reports presented some of the first evidence that patients with *NRG1* gene fusions who were treated with afatinib had durable responses.[5] While the first reports emerged in lung cancer,[5] further research has implicated other solid tumors.[6] These findings indicate that malignancies associated with *NRG1* gene fusions may benefit from treatment with afatinib.

Afatinib (Gilotrif®) was initially approved in 2013 by the U.S. Food & Drug Administration (FDA) for the first-line treatment of patients with metastatic NSCLC whose tumors have EGFR exon 19 deletions or exon 21 (L858R) substitution mutations; this indication was broadened in 2018 to include non-resistant EGFR mutations. Additionally, afatinib was approved in 2016 for the treatment of patients with metastatic squamous NSCLC progressing after platinum-based chemotherapy. Obtaining real-world data describing the real-world outcomes associated with afatinib use in patients with *NRG1* fusion-positive across a range of solid tumors may be used in supplemental applications for label expansion requests to the FDA and other agencies. This study aims to provide real-world evidence on the real-world clinical outcomes associated with afatinib use among patients with *NRG1* gene fusions across a range of solid tumors, as well as real-world data among patients with *NRG1* gene fusions treated with other systemic therapies.

8. RESEARCH QUESTIONS AND OBJECTIVES

Limited data on durable responses in patients with *NRG1* gene fusion-positive solid tumors have been reported with afatinib. Beyond these data, no comprehensive evaluation has been conducted of patients harboring *NRG1* gene fusions treated with afatinib or other systemic therapy, in any line of therapy, to describe patient characteristics and clinical outcomes associated with afatinib use. This study aims to answer these questions by achieving the objectives stated below. As this study is descriptive in nature, no *a priori* hypothesis will be tested.

Research Questions:

1. What are the characteristics of patients with *NRG1* gene fusion-positive solid tumors treated with afatinib, and what are the characteristics of those treated with another systemic therapy?

Study Objectives:

1. To describe the demographic and clinical characteristics of patients with *NRG1* gene fusion-positive solid tumors treated with afatinib and of patients with *NRG1* gene fusion-positive solid tumors treated with other systemic therapy.
2. To calculate the ORR and DOR among patients with *NRG1* gene fusion-positive solid tumors treated with afatinib and among patients with *NRG1* gene fusion-positive solid tumors treated with other systemic therapy
3. To estimate PFS (and TOT, TTP) among patients with *NRG1* gene fusion-positive solid tumors treated with afatinib and among patients with *NRG1* gene fusions treated with other systemic therapy
4. To estimate OS among patients with *NRG1* gene fusion-positive solid tumors treated with afatinib and among patients with *NRG1* gene fusion-positive solid tumors treated with other systemic therapy
5. To describe the incidence and severity of AEs among patients with *NRG1* gene fusion-positive solid tumors while on treatment with afatinib or other systemic therapy

9. RESEARCH METHODS

9.1 STUDY DESIGN

This is a non-interventional, retrospective, US, multi-site, cohort study based on existing data from medical records of patients with *NRG1* gene fusion-positive solid tumors treated with afatinib or other systemic therapy. Two cohorts of patients will be identified. The first includes any patient with *NRG1* gene fusion-positive solid tumors who has received afatinib in any line of therapy (afatinib cohort) between 01/01/2017 and 03/31/2020. The second includes any patient with *NRG1* gene fusion-positive solid tumors who has not received afatinib in any line of therapy (other systemic therapy cohort) during the same period and no history of afatinib use. Follow-up will include at least 3 months after initiation of afatinib or other systemic therapy, unless a patient died prior to 3 months of follow-up.

In total, up to 120 patients with *NRG1* gene fusion-positive solid tumors will be selected for this study, of whom up to 70 will be afatinib-treated and up to 50 will be treated with other systemic therapy. Study objectives are to describe these patients and calculate the ORR in each group, as well as to estimate PFS, TOT, TTP, OS, DOR, and DOCB along with describing the incidence and severity of AEs among patients in the two cohorts. Data to be collect through this medical chart review include patient demographics, clinical characteristics at the time of diagnosis/initiation of a line of therapy, treatment-related data points (dates of initiation, discontinuation, dosing), AEs occurring during therapy, disease response, date of progression and/or death.

Given the small number of patients targeted for study inclusion and anticipated differences in baseline characteristics between afatinib-treated and patients treated with other systemic therapies, statistical comparisons are not planned. In lieu of statistical comparisons between cohorts, the non-afatinib arm will provide context for interpreting results among those treated with afatinib. Specifically, this context includes what patients with *NRG1* gene fusions not treated with afatinib look like, how they are managed and treated, and what their clinical outcomes look like. The non-afatinib arm will provide a broader understanding of *NRG1* gene fusions among patients with solid tumors

Data collection is anticipated to begin in the third/fourth quarter of 2020, allowing for a minimum follow-up period of 3 months. All patients are required to have initiated index therapy (i.e., afatinib in any line; other systemic therapy among those without any history of afatinib) between 01/01/2017 and 03/31/2020. As such, the maximum follow-up period is approximately 39 months. The index date is the date of initiation of afatinib or other systemic therapy between 01/01/2017 and 03/31/2020 for the other systemic therapy cohort.

9.2 SETTING

Approximately 20 or more unique providers will participate in this research study. To minimize potential bias, the maximum number of patients each provider may select and complete data abstraction for is capped at 30; for any provider who submits >10 patients, their data will be reviewed in detail by a clinician and analyst to identify any data quality issues (see Section **9.8.2 Data Validation** for further details on data quality assurance and control measures). Data

will be collected through an electronic case report form (eCRF) completed by the patients' providers who volunteer to participate in the study. Providers will be compensated at fair market value for the time to complete data abstraction and quality control procedures, which are estimated to take up to 1 hour per patient.

Recruitment of providers will be conducted electronically. Providers who responded to an initial feasibility request and reported treating potentially eligible patients will be contacted and invited to participate. Recruitment to fill the up-to-120-patient quota will run for 4 weeks from the date of recruitment launch. During that time, the per-cohort quotas will be electronically monitored to ensure that the final number of patients achieves up to 70 patients with *NRG1* gene fusion-positive solid tumors treated with afatinib and up to 50 with an *NRG1* gene fusion-positive solid tumor not treated with afatinib at the time of data collection. As recruitment for a cohort is completed, no further patient data entry will be allowed for that cohort; however, providers actively completing an eCRF at the time of quota close for a cohort will be allowed to complete that eCRF, and the total number of patients per cohort may exceed the quotas.

Providers will be asked to identify all eligible patients, and starting with the earliest index date, chronologically select consecutive patients meeting the eligibility criteria and complete the data abstraction. The eCRF is structured to allow data collection regarding patient clinical history at the time of initial diagnosis of their solid tumor, initiation of index therapy (including dates of dose starts, stops, and interruptions), response to therapy, dates of disease progression, AEs, (including dates of onset, recovery, and reported deaths).

9.2.1 Provider/Site/Patient Selection

Provider Eligibility

Providers who meet the following criteria will be eligible to participate:

- 1) Are board-certified oncologist/hematologist.
- 2) Have treated/are treating at least one eligible patient with an *NRG1* fusion-positive solid tumor.
- 3) Are able to participate in research approved by an external institutional review board (IRB).
- 4) Agree to participate in data quality assurance/control processes.

Providers will select patients meeting the study eligibility criteria as described below. Providers will be asked to select eligible patients chronologically, starting with the first patient who first initiated any line of afatinib or chemotherapy, on or after 01/01/2017 through 03/31/2020.

Patient Eligibility

Inclusion Criteria:

- Adults, 18 years of age or older, at the time of diagnosis with any solid tumor.
- Confirmed *NRG1* gene fusion in any solid tumor.
- Initiated afatinib or other systemic therapy (in any line of therapy) for treatment of a solid tumor with *NRG1* gene fusion on or after 01/01/2017 through 03/31/2020.

- Followed up for ≥ 3 months after initiation of afatinib or other systemic therapy (unless deceased prior to 3 months of follow-up).

Exclusion Criteria:

- Treatment with any TKI/ErbB-directed therapy other than afatinib

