9.3.2 Outcomes

Demographic and clinical characteristics of patients with *NRG1* gene fusion-positive solid tumors treated with afatinib and of patients with *NRG1* gene fusion-positive solid tumors treated with other systemic therapy will be summarized for each cohort. These variables serve as outcomes in terms of fulfilling study objectives. These variables also serve as covariates to contextualize other study outcomes (e.g., ORR, DOR, DOCB, PFS, TOT, TTP, OS, AEs).

Table 1. Patient demographics and clinical characteristics.

Characteristic	Definition
Sex	Patient sex, as charted
Age(s)	Age at diagnosis of solid tumor and age at initiation of afatinib or other systemic therapy
Region	US census region of patient: Northeast, South, Midwest, West
Race/ethnicity	Race and ethnicity of patient, as charted
Tumor type	Description/classification of primary tumor of patient (e.g., NSCLC, cholangiocarcinoma, pancreatic cancer)
ECOG PS	ECOG PS of patient at initiation of afatinib or other systemic therapy
Comorbidities	Comorbidities present at initiation of afatinib or other systemic therapy, following Charlson comorbidity index
Stage	Stage of tumor at initiation of afatinib or other systemic therapy
NRG1 results	Date of NRG1 gene fusion test; laboratory performing test (e.g., academic, reference, in-house lab; name of lab); NRG1 gene fusion partner
Other biomarkers	Tumor-specific biomarkers tested and their results (e.g., MSI/MMR, EGFR, HER2)

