DOR	Duration of response will be calculated as the time from initial response (for any patient with a complete or partial response initially) until the earliest of either disease progression or death. Patients who discontinue therapy due to a reason other than progression will be censored on the date of discontinuation. Patients still on therapy at the time of data cut-off will be censored on their last visit date.
TOT	Time from initiation of a line of therapy until discontinuation for any reason; patients on therapy at the time of data cut-off will be censored on the last date of treatment.
TTP	Time from initiation of a line of therapy until discontinuation due to disease progression; patients on therapy or those who discontinued due to a reason other than disease progression will be censored on the last date of treatment.

PFS	Time from initiation of a line of therapy until disease progression or death; patients on therapy at the time of data cut-off will be censored on the last date of treatment. Patients who discontinue a line of therapy for a reason other than disease progression but who subsequently die prior to the receipt of any other therapy will be considered an event on the date of death.
OS	Time from initiation of any therapy in the metastatic setting until death; patients alive at the time of data cut-off will be censored on the last date the patient was seen by the provider/clinic.
AE	An adverse event is defined as any untoward medical occurrence in a patient administered a medicinal product and which does not necessarily have a causal relationship with this treatment. AEs from a prepopulated list (including “other, please specify”) during each line of therapy will be indicated by providers. The number and proportion of patients experiencing each AE reported during afatinib or other systemic therapy will be reported. See Section 11.1 and Table 3 for further details.

In addition to TOT, to further characterize treatment patterns for those treated with afatinib and those treated with other systemic therapy, the following will be collected (and calculated based on the collected data):

- Treatment history (i.e., regimens, duration, number of cycles, sequence)
- Starting dose of afatinib or other systemic therapy
- Dose modifications of afatinib or other systemic therapy (i.e., dose reductions and their timing, dose increases and their timing, dose delays and their duration and timing)

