9.7 DATA ANALYSIS

Demographic and clinical characteristics will be reported by descriptive analyses including counts and frequencies for dichotomous and categorical variables, while measures of centrality (mean, median) and spread (min, max, standard deviation, interquartile range, as appropriate) will be used for continuous variables. These characteristics will be described at the time of initial diagnosis of advanced/metastatic disease and at the time of initiation of each line of therapy received, for the afatinib cohort and separately for the other systemic therapy cohort. No statistical comparisons will be made across these two cohorts in terms of demographic, clinical characteristics, and clinical outcomes.

The calculations for all outcomes (e.g., ORR, DOR, DOCB, TOT, TTP, PFS, OS) are defined in **Table 2** in Section **9.3.2 Outcomes**. For disease response, the point estimate for ORR and associated 95% confidence interval (CI) will be calculated for initial response to index therapy (i.e., afatinib or other systemic therapy) and best response to index therapy, for each cohort. ORR will be reported among subgroups within each of the treatment cohorts, by tumor type and line of therapy. The Kaplan-Meier method will be used to estimate time-to-event outcomes (DOR, DOCB, TOT, TTP, PFS, and OS) to account for any right-censoring (e.g., patient had not discontinued therapy, patient had not progressed, or died). Time-to-event outcomes will be described for each of the two treatment cohorts and in subgroups within the two treatment cohorts, according to solid tumor and line of therapy. All study outcomes will be reported separately for those treated with afatinib monotherapy. In the event an outcome cannot be assessed for a given patient, that patient would be omitted from assessment of that outcome; reason for omission in a given outcome assessment will be reported.

Cumulative incidence, severity, and timing of AEs during the index therapy will be summarized and displayed in number/percentage form for each of the treatment cohorts, separately. All safety endpoints will be analyzed descriptively. AE reporting is summarized in Section **11 Management and Reporting of Adverse Events/Adverse Reactions**.

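### OS, and the death part of PFS, can include guaranteed survival time: the NRG1 result may come after therapy began, the OS clock may start before index therapy, and only right-censoring is handled.

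*Combined protocol and SAP*

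**What the plan says.** **Eligibility (Section 9.2.1).** One criterion is "Confirmed *NRG1* gene fusion in any solid tumor". Another is "Initiated afatinib or other systemic therapy (in any line of therapy) for treatment of a solid tumor with *NRG1* gene fusion", within the calendar window. Neither states an order between the test result and the start of therapy.

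**Time origins.** Section 9.1 says: "The index date is the date of initiation of afatinib or other systemic therapy between 01/01/2017 and 03/31/2020". In Table 2 (Section 9.3.2), PFS is "Time from initiation of a line of therapy until disease progression or death", and TTP and TOT also start with the line. OS is different: "Time from initiation of any therapy in the metastatic setting until death". Index therapy may be given in any line, so the OS clock can start well before the index date in either cohort.

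**Analysis (Section 9.7).** "The Kaplan-Meier method will be used to estimate time-to-event outcomes (DOR, DOCB, TOT, TTP, PFS, and OS) to account for any right-censoring". Delayed entry and left truncation are not mentioned.

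**Test date.** Table 1 collects the date of the "gene fusion test; laboratory performing test", and the Abstract lists test timing among the characteristics to be described. Section 9.7 gives the date no role in the outcome analyses.

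**The concern.** Entry to the sample depends on events that can happen after the survival clock starts. There are two routes.

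1. **Late testing.** A patient tested after therapy began enters only by living to the result. A similar patient who died untested has no confirmed fusion and is never counted.
2. **Gap to index therapy.** A patient whose index therapy is a later metastatic line enters only by living to that line, yet OS runs from the first one.

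In both cases the Kaplan-Meier risk set in the early months holds people who, by construction, could not have died then, so the OS curve sits too high. The same applies to deaths counted as PFS events between line start and a late test.

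The study is descriptive, so the estimates are the product. OS is Objective 4. Section 7 says the data may support label-expansion requests, and Section 9.1 uses the second cohort as context for the afatinib results. If the two routes affect the cohorts unequally, that context is distorted even though no test is planned.

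**Working it through.** The plan states no figure to reproduce here. The check compares the definitions and then sizes the bias under stated assumptions.

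**Does another provision close the gap?**
- Patients who died within 3 months of starting therapy stay eligible (Abstract, Section 9.2.1), but they still need a confirmed fusion. This rule does not bring in those who died untested.
- The example date check in Section 9.8.2 compares index start with cancer diagnosis, not with the NRG1 test.
- Sections 9.9 and 9.12 discuss provider and patient selection, but neither left truncation nor guaranteed survival.

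**Model (all inputs assumed).** OS is exponential with median 12 months, so λ = ln 2 / 12 = 0.0578 per month. A share p of fusion-positive patients must wait an exponential time with mean m (rate μ = 1/m) before they can enter. Let q = λ/(λ+μ), the chance of dying during the wait. Without censoring, the curve counted from the early origin is

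S(t) = [exp(−λt) − p·q·exp(−(λ+μ)t)] / (1 − p·q).

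*Late testing, p = 0.5, m = 3.* q = 0.0578/0.3911 = 0.148 and p·q = 0.0739. At t = 13.3, S = (0.4638 − 0.0004)/0.9261 = 0.50. The apparent median is 13.3 months against a true 12.

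*Gap to index therapy, p = 1, m = 6.* q = 0.257. At t = 16.9, S = (0.377 − 0.006)/0.743 = 0.50. The apparent median is 16.9 months.

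**Late testing, simulated** with 600,000 patients per scenario and uniform censoring at 3 to 42 months. True median 12 months:

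| Share untested at start | Mean delay (months) | Kaplan-Meier from therapy start | Delayed entry at test |
|---|---|---|---|
| 0% | – | 12.0 | 12.0 |
| 25% | 3 | 12.6 | 12.0 |
| 25% | 6 | 12.9 | 12.0 |
| 50% | 3 | 13.3 | 12.0 |
| 50% | 6 | 13.9 | 11.9 |
| 75% | 3 | 13.9 | 11.9 |
| 75% | 6 | 15.2 | 12.0 |

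Survival at 12 months reads 0.52 to 0.59 instead of 0.50. The ranges are 9.6 to 11.9 for a true median of 9, and 18.6 to 21.5 for a true median of 18.

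**Gap from first metastatic therapy to index therapy** (no censoring, everyone must reach index). Mean gaps of 3, 6 and 9 months give apparent medians of 14.8, 16.9 and 18.5 against a true 12. Delayed entry at the test date alone does not remove this when the test came first; entry must also wait for index start.

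**If progression prompts the test.** Entry time then depends on prognosis, and delayed entry loses its justification. In an assumed model with testing soon after progression and a higher death hazard thereafter, the true median was 11.6. Kaplan-Meier from therapy start gave 11.8 to 12.4, and delayed entry gave 10.9 down to 9.0. Restricting to patients tested by time zero gave about 11.6.

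**The case against.** **The fusion may be meant to be known at start.** The treatment criterion can be read as therapy directed at a tumor already known to carry the fusion. The wording describes the tumor, however, not what was known when therapy began. If knowledge was intended, one clause would settle late testing. It would not settle the OS origin.

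**Test timing is already described.** This is true, and it makes part of the fix a small extension. A descriptive table does not correct the OS curve.

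**The size is assumed and small beside sampling error.** The late-testing shift is 0.6 to 3.2 months (12.6 − 12 and 15.2 − 12). At n = 50, a simulated 95% sampling range for a 12-month median is about 7.6 to 18.7. This stands as a caution on magnitude. A one-directional error still does not average out, and the confidence interval will not show it.

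**Delayed entry can do harm.** This stands. If progression triggers testing, it overshoots downward and can be further from the truth than the planned estimate. It should not be the only remedy, and its assumption must be stated.

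**Splitting outcomes by test timing conditions on a later event.** This is right for a separately reported late-tested group. A restriction to patients tested on or before index start uses only what was known at time zero.

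**A wider reading is tempting:** that every time-to-event outcome contains guaranteed time. The definitions do not support it. Progression or discontinuation can occur before a late test, so TTP and TOT are not protected over that interval. DOR and DOCB start at response.

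**Conclusion.** The point holds for OS and for the death component of PFS. The plan allows entry conditions to be met after time zero and has no provision for left truncation. The resulting bias in OS is upward; every scenario run showed this.

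Its size for this study cannot be derived, because the documents give neither the share tested late nor the delays. For a true 12-month median, the illustrations are 12.6 to 15.2 months for late testing and 14.8 to 18.5 months for the gap to index therapy. They rest on exponential survival and on delays independent of prognosis.

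Three further inferences go beyond the documents:
- **That late testing did occur, or is concentrated in the other-therapy cohort.** This is plausible, since that therapy need not have been chosen because of the fusion, but no timing data are given.
- **That index-line PFS, TTP and ORR are biased downward.** This follows only if progression prompted the test.
- **That delayed entry cures the problem in general.** It does so only if test timing is independent of prognosis.

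A tumor tested after death from stored tissue would be an exception to the late-testing route; the documents do not mention it.

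**What to change.** Amend Section 9.7, and the OS row of Table 2 if the origin changes:

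1. **OS.** Estimate it from index therapy start. If the metastatic-therapy origin is kept, use Kaplan-Meier with delayed entry at the latest of time origin, NRG1 result date and index start, and state that this assumes test timing is independent of prognosis. Moving the origin to index start removes the gap but not the effect of testing after index; item 3 covers that part.
2. **Test timing.** Tabulate by cohort the number of patients tested after index start and the interval from result to index.
3. **Sensitivity analysis.** Report OS from index start, PFS and ORR restricted to patients whose NRG1 result came on or before index start. This makes no assumption about why others were tested late.

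If the fusion was always meant to be known at start, say so in Section 9.2.1; late testing then falls away, and only the OS origin needs the change in item 1.

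No new variable is needed, since test, treatment and death dates are already collected. The costs are smaller and less stable early risk sets under delayed entry, and a smaller sample in the restricted analysis, from cohorts of at most about 70 and 50 that are already subdivided by tumor type and line.

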The ORR among patients with *NRG1* gene fusion-positive solid tumors treated with afatinib and among patients with *NRG1* gene fusion-positive solid tumors treated with other systemic therapy will be calculated as the proportion of patients with a complete response (CR) or partial response (PR) out of all patients (CR+PR/all patients) (see **Table 2** below). Disease response for determining the ORR will be reported as recorded in the patient's EHR, including the date of radiographic imaging used to substantiate the patient's initial and best response to therapy. Providers will indicate whether the patient experienced a CR, PR, stable disease (SD), or progressive disease (PD). No independent blinded review of radiology studies will be conducted. Lesion measurements at baseline (initiation of afatinib; initiation of other systemic therapy for non-afatinib treated patients), initial response, and best response will be abstracted as available. Changes in the number, locations, and sizes of lesions at initial and best response to therapy will be evaluated by [REDACTED] using RECIST v1.1 guidelines. The sum of lesion measurements will be assessed at baseline and at follow-up scans to calculate the percent change in sum of target lesions, as well as account for new lesions on follow-up scan in order to classify response by RECIST v1.1 criteria. Actual scan images will not be reviewed; the calculation of real-world disease response will be based on the lesion measurements provided. Other outcomes include PFS, TOT, TTP, OS, DOR, DOCB, AEs. Definitions of these outcomes are shown in **Table 2**.

Table 2. Study outcomes and definitions.

Outcome	Definition
ORR	Proportion of patients with a complete response (CR) or partial response (PR) out of all patients (CR+PR/all patients) at initial response assessment and best response
DOCB	Duration of clinical benefit (DOCB) will be calculated as the time from initial response (for any patient with a complete, partial, or stable disease response initially) until the earliest of either disease progression or death. Patients who discontinue therapy due to a reason other than progression will be censored on the date of discontinuation. Patients still on therapy at the time of data cut-off will be censored on their last visit date.

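### Adjuvant and neoadjuvant courses can qualify as index therapy, although the OS definition and the baseline description presuppose advanced or metastatic disease

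*Combined protocol and SAP*

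**What the plan says.** Section 9.2.1 (and the Abstract, Population) admits adults with a confirmed NRG1 fusion in any solid tumor who "Initiated afatinib or other systemic therapy (in any line of therapy) for treatment of a solid tumor with" that fusion within the window and meet the follow-up rule. The only exclusion is "Treatment with any TKI/ErbB-directed therapy other than afatinib". Stage, resectability, treatment intent and measurable disease are not mentioned.

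Section 9.1 is equally open: "The index date is the date of initiation of afatinib or other systemic therapy between 01/01/2017 and 03/31/2020".

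Section 9.3.2, Table 1, lists "Stage of tumor at initiation of afatinib or other systemic therapy" as a descriptive variable. Table 2 measures PFS, TTP and TOT from the start of a line of therapy in any setting, but defines OS as "Time from initiation of any therapy in the metastatic setting until death". ORR is the proportion of responders "out of all patients (CR+PR/all patients) at initial response assessment and best response".

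Section 9.7 says of demographic and clinical characteristics: "These characteristics will be described at the time of initial diagnosis of advanced/metastatic disease", and also at the start of each line. The Abstract repeats this. Section 9.7 plans subgroups by tumor type and line of therapy only. It also says that a patient whose outcome cannot be assessed is left out of that outcome, with the reason reported.

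**The concern.** The eligibility rules and the outcome rules describe different populations. Consider a resected patient given postoperative chemotherapy in the window. She is eligible for the other-therapy cohort and has a PFS time, but that time is really disease-free time. Her time on treatment reflects a course given after resection rather than treatment of measurable tumor. She has no OS origin unless she is later treated for metastatic disease, and then her OS clock starts at a course other than her index course. She also has no date of advanced diagnosis at which to be described.

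At stake is what Objectives 2 to 4 estimate. Pooled PFS would mix two disease courses, and PFS and OS could refer to different patients or different treatments without the report saying so. The other-therapy cohort is there to give context for the afatinib results, and Section 7 says the data may support label-expansion requests. A context estimate that depends on an uncontrolled mix of settings is hard to use for either purpose.

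**Working it through.** **1. Which rules catch a perioperative-only patient**

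| Rule | Place | Result for this patient |
|---|---|---|
| Inclusion and exclusion | 9.2.1 | Eligible |
| Index date | 9.1 | Start of the perioperative course |
| PFS, TTP, TOT | Table 2 | Clock starts at that course |
| OS | Table 2 | No origin, or origin at a later course |
| Baseline description | 9.7 | No advanced-disease date; start-of-line date only |
| ORR, neoadjuvant | Table 2 | Included; tumor is present and can respond |
| ORR, adjuvant | Table 2 against 9.7 | Counted under all patients; dropped under the omission rule |
| Subgroups | 9.7 | Tumor type and line; not setting |

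**2. Illustration for PFS.** None of these inputs is in the documents. Assume exponential times, median 6 months in advanced disease, median 36 months after resection, and a perioperative share f of 10%, 20% or 30%.

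*Full follow-up.* The pooled median t solves (1−f)·2^(−t/6) + f·2^(−t/36) = 0.5.

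*Censored when the course ends, assumed at 4 months.* Up to month 4 both groups contribute, so S(4) = (1−f)·2^(−4/6) + f·2^(−4/36) = (1−f)·0.630 + f·0.926. After month 4 only advanced patients remain at risk, so the Kaplan-Meier median is 4 + 6·log2(S(4)/0.5).

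| f | Median, full follow-up | S(4) | Median, censored at 4 months |
|---|---|---|---|
| 0 | 6.0 | 0.630 | 6.0 |
| 10% | 6.8 | 0.660 | 6.4 |
| 20% | 7.7 | 0.689 | 6.8 |
| 30% | 9.0 | 0.719 | 7.1 |

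Under full follow-up, varying the post-resection median from 18 to 36 months gives 6.6–6.8, 7.2–7.7 and 8.0–9.0 months. In all of these cases the pooled median rises.

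**3. Illustration for ORR.** Assume 30% in advanced disease, and assume that every perioperative patient is a non-responder kept in the denominator. Then ORR = 0.30·(1−f) = 27%, 24%, 21%. If non-assessable patients are omitted instead, adjuvant courses cause no fall. Neoadjuvant patients can respond, so their effect could go either way.

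**4. Precision cost of restricting.** The plan's Table 4 gives ±10.7% at n=70 and ±12.7% at n=50 for a proportion of 30%. Both reproduce as 95% half-widths, 1.96·√(0.3·0.7/n) = 10.74% and 12.70%, although the table labels them SE. Removing 10%, 20% or 30% of patients gives:

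- n=70 falls to 63, 56, 49: ±11.3%, ±12.0%, ±12.8%.
- n=50 falls to 45, 40, 35: ±13.4%, ±14.2%, ±15.2%.

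**The case against.** The strongest reply is that Section 9.7 already removes patients whose outcome cannot be assessed. A resected patient with no lesion fits that rule for ORR, and a patient with no metastatic therapy fits it for OS. This stands in part. A reader might infer that adjuvant courses necessarily pull ORR down, and the documents do not support that. They leave the all-patients definition and the omission rule in conflict. The rule does not help with PFS, where the patient is assessable, or with neoadjuvant courses in ORR.

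Second, the PFS shift depends on follow-up after treatment ends. Table 2 counts a death before any further therapy as a PFS event, but does not say how other patients who stop without progression are handled. This stands, and is why both versions are shown.

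Third, a reader might infer that selecting from the earliest index date makes a patient's curative-intent course the likely index. Sections 9.2 and 9.2.1 order patients, not courses within one patient. A reader might also infer that perioperative courses fall mainly in the other-therapy cohort. That is plausible, since the afatinib approvals described in Section 7 are for metastatic NSCLC, but this study looks beyond those indications and gives no counts.

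Finally, stage at index is collected, outcomes are split by tumor type and line, and no comparison between cohorts is planned. No planned contrast is therefore biased. But stage and line do not identify treatment intent, and each cohort's own PFS and OS remain hard to interpret.

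**Conclusion.** The mismatch is real and can be read directly from the text: perioperative courses are allowed as index therapy, while OS and part of the baseline description presuppose advanced or metastatic disease. For any such patient, PFS and TOT are not comparable with those of the rest of the cohort, and OS has no origin or a different one. The text shows that these patients may enter, not that they will.

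The size is illustrative only. A 10% to 30% share moves an assumed 6-month median PFS to about 6.8–9.0 months with full follow-up, or 6.4–7.1 months with censoring at an assumed 4 months. ORR falls from an assumed 30% to 27–21% only if these patients are non-responders kept in the denominator. A reader might take this as a defect that invalidates Objectives 2 to 4. Without a known share, and with no comparison planned, the documents do not support that. It is a drafting gap that should be fixed, and that can be closed before data are collected.

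**What to change.** Before data collection, take one of two routes.

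- **Restrict eligibility.** Add to Section 9.2.1 and the Abstract that index therapy was given for metastatic disease, or for locally advanced disease not treated with curative-intent resection. Record perioperative courses as treatment history only, and add an eCRF logic check.
- **Keep eligibility broad.** Add an eCRF field for treatment setting and intent, because stage alone cannot separate perioperative from advanced-disease treatment. Restrict ORR, DOR, DOCB, PFS, TTP and OS to index courses given for advanced or metastatic disease, and report the remaining patients separately.

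On either route, align the OS origin with the index population, and state one ORR denominator rule that reconciles Table 2 with the omission rule in Section 9.7.

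The cost is one eligibility line or one eCRF field. A few early-stage patients would no longer count toward the quotas, and intervals would widen slightly: at an assumed 10% share and 30% ORR, from ±10.7% to ±11.3% in the afatinib cohort and from ±12.7% to ±13.4% in the other. Section 6 places protocol finalization in July 2020 and data collection in Q3/Q4 2020, so the change fits the schedule. If it is left open, the choice would have to be made after outcomes are visible.
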